C.5.b. Intervention Process: Focused on HPV vaccine initiation. Through BCT, we will select a set of HPV vaccine initiation reminders to encourage uptake among age- and vaccine-eligible adolescents. Reminders could include letters (with strong provider recommendations, and bundled recommendations), text messages with links to digital stories, patient and/or P/C narratives, letters, automated phone calls, or email messages. Because we hope to implement this trial as part of standard care, our study will apply to obtain a waiver of informed consent, which was successful in STOP CRC because intervention components are similar to primary health care settings' standards of care and imply minimal risk (See Section C.2). Sea Mar analysts will create a real-time list of patients due for an initial HPV vaccine dose, and the clinic outreach coordinator will review the list and remove any patients missing telephone number or address (if a mailed intervention is selected). P/C of remaining children and adolescent patients (i.e., participants) will be individually randomized to either Auto or Auto-Plus intervention or UC, in a 1:1:1 ratio. The PREVENT study will only target one child/adolescent per parent/caregiver (siblings will be excluded from intervention assessments). In Sea Mar clinics, 87% of phone numbers of patients eligible for CRC screening (aged 50-75) could receive text messages; we expect a higher percentage for the younger cohort in this trial.88 Participant lists will be sent to Sea Mar's communications vendor (ClienTell) for delivery of automated HPV vaccine initiation prompts; the UC group will not receive tailored reminders but will only receive opportunistic vaccine reminders that are delivered during clinic visits or MyChart EHR-based patient portal reminders. As in STOP CRC, real-time participant lists will be refreshed to discontinue reminders for P/C of patients who have received a given vaccine dose.

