Consistent with the desire of clinic staff to integrate this project into their standard workflows, we will use automated codes to manage interventions so that eligible patients get initial HPV vaccines on time and P/C are prompted to repeat vaccination, as recommended. Our EHR tools rely on Reporting Workbench, a population management tool in Epic which will be customized to include tools needed for tracking completion of HPV vaccination at the 4 intervention clinics. The registry will list patients' HPV vaccination history as well as key demographic variables for the intervention (e.g., name, address, preferred language). We will select a cohort of approximately 1,038 P/C of patients from the 4 clinics, randomized to intervention arms (UC, Auto, and Auto-Plus) stratified by clinic, sex, and language preference (English, Spanish, other) to ensure a nearly balanced distribution of clinic, sex, and language preference among study arms. The registry will generate 2 real-time reports: 1] HPV vaccination outcomes (i.e., date of vaccination events, and whether the event represents series initiation, second dose, and/or series completion); and 2] PREVENT intervention activities (i.e., date of

Table 3: Schedules of Measures (part.=participants; T=time, Y=year; M=month)								
Variable	Data source	How measured	Proctor/ RE- AIM domain	Т				
Aim 1: Bootcamp Translation (BCT)								
Rural parent-/ caregiver- & provider-driven adaptations/ program acceptance	Parents / providers	Notes from BCT sessions	Adaptations, Acceptance	Y 1				
Aim 2: PREVENT Randomized 0	Controlled Trial (I							
Reach of RCT – primary outcome (next needed HPV vaccine dose)	EHR; vendor logs	N part. receive program/ N anticipated, reasons	Reach	6 m				
Reach of RCT – secondary outcome (completion of HPV vaccine series)	EHR; vendor logs	N part. receive program/ N anticipated, reasons	Reach	6 m				
Effectiveness of RCT – primary outcome	EHR	N C/A complete next HPV vaccine dose/ N anticipated	Effectiveness	6 m				
Effectiveness of RCT – secondary outcome	EHR	N C/A complete all doses of HPV vaccine  / N anticipated	Effectiveness	13 m				
Aim 3: Tertiary and Qualitative	Outcomes							
Moderators (e.g., sex of parent, sex of child, age, ethnicity, etc.)	EHR data	Effectiveness of intervention by presence of moderator	Equity	6 m				
Parent/caregiver reactions	Interviews	Coded transcripts	Acceptance	Y 3				

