- Interactive web-based coaching tool: Live calls will be facilitated by an interactive web-based coaching tool that prompts patient navigators during live phone calls with P/C on how to best respond to varying types and levels of P/C vaccine hesitancy. This tool will be developed by Drs. [name] and [name] in partnership with HCl's bioinformatics core. P/C identified vaccine hesitancy barriers may fall within the broad domains related to vaccine confidence, vaccine complacency, and vaccine convenience (Figure 2).
- Patient navigators: trained staff who promote healthful behaviors by addressing barriers to care. Navigators can respond to the cultural needs of their patients—such as values of *personalismo* or *respeto*. 127, 128

**C.5.c.** Intervention Process: Focused on HPV vaccine series completion. The BCT process will define the format (mode and frequency) and content of messages to promote vaccine series completion. The clinic-level analysts will generate real-time lists of patients who have initiated the HPV vaccine and are due for a follow-up dose, stratified by age group (11–14 vs. 15–17). The list will include adolescents age 11–14 years who have completed an initial dose of the HPV vaccine and are due for a second dose (within 6-12 months) and those aged 15–17 who are due for a second or third dose. While Auto and Auto-Plus interventions for series

completion may use some of the same components as vaccine initiation (automated calls, live calls, text messages, emails, and mailings), some notable differences will likely exist. HPV vaccine initiation may bundle recommendations for HPV and for other needed vaccines (e.g., "[Patient name] is due for the following vaccines: HPV; meningococcal; Tetanus, Diphtheria, Pertussis"), whereas series completion will not need bundled messages. Series completion reminders will include scheduling and appointment reminders.

**C.5.d. Evaluation:** Based on our previous research and conversation with clinic staff, we have designed Phase I to include multiple components. Using the Proctor Implementation and RE-AIM frameworks, we will track intervention reach and effectiveness. We will conduct one-on-one interviews with participants and debrief interviews with HCP to illuminate persistent barriers to HPV vaccination uptake and factors important to program acceptability, maintenance, and sustainability. **Table 3** summarizes these measures.

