Program Effectiveness: We will assess intervention effectiveness for each of the three study arms, calculated as the proportion of eligible children/adolescents who received any HPV vaccine within 6 months and 13 months (series completion by one year) of randomization. We will assess the proportion of C/A who initiated HPV vaccination, those who received the next needed dose and the percent who completed the series.

Study Design: We propose a 3-arm RCT to compare rates of completing the next step in the HPV vaccination series at 6 months and completing the HPV vaccination series at 13 months between Auto, Auto-Plus, and UC arms. P/C of C/A who have not completed the HPV vaccination series will be randomized 1:1:1 to study arms, with separate randomizations within each clinic (Ocean Shores, Aberdeen, Elma, or Yelm) and patient-level HPV vaccination initiation status (series initiated or not initiated). Participants will be assessed for eligibility and, if eligible, enrolled within the 4 clinics at their first visit time during the 12-month study period, with a total participant time on study of 13 months, for a total of 25 months of enrollment, execution, and follow-up.

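### Randomisation is list-based in C.5.b but tied to a clinic visit in C.5.d; the visit rule narrows entry to attenders and can credit enrolment-visit doses that no reminder could have caused

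*Combined protocol and SAP*

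**What the plan says.** **List or registry entry (C.5.b).** "Sea Mar analysts will create a real-time list of patients due for an initial HPV vaccine dose". Patients without contact details are removed, and then "P/C of remaining children and adolescent patients (i.e., participants) will be individually randomized to either Auto or Auto-Plus intervention or UC". The same section says that "our study will apply to obtain a waiver of informed consent", so no enrolment encounter is required. Further on it describes entry as a registry selection: "We will select a cohort of approximately 1,038 P/C of patients from the 4 clinics, randomized to intervention arms".

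**Visit entry (C.5.d, Study Design).** "P/C of C/A who have not completed the HPV vaccination series will be randomized 1:1:1 to study arms". Those found eligible are to be "enrolled within the 4 clinics at their first visit time during the 12-month study period". Each participant is then followed for 13 months, giving 12 + 13 = 25 months in all.

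**Clock and endpoint (C.5.d, Program Effectiveness).** The proportion is based on any HPV vaccine received within 6 and 13 months of randomisation. No rule covers a dose given on the day of randomisation.

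**Usual care (C.5.b).** Control participants "will only receive opportunistic vaccine reminders that are delivered during clinic visits or MyChart EHR-based patient portal reminders".

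**Reminder lists for later doses (C.5.c).** Analysts produce "real-time lists of patients who have initiated the HPV vaccine and are due for a follow-up dose". This section concerns reminders and does not mention randomisation.

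**The concern.** The trial tests outreach that reaches families outside a visit. If entry waits for a visit, two things change.

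First, the population becomes patients who attend one of the four clinics in a 12-month window, not patients identified from the record as needing a dose. Families who do not attend never enter.

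Second, the visit is itself an occasion for vaccination in every arm, since usual care includes opportunistic prompting at visits. If the participant is randomised and then vaccinated at the same visit, the primary outcome is met before any automated message could have had an effect. The extra Auto-Plus contact comes later still: it is for patients still unvaccinated after 3 weeks. Such participants add equal successes to all arms and pull the difference towards zero.

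The sites or analysts could also follow different sections and so use different entry events and time zeros. That is hard to repair once randomisation has begun.

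**Working it through.** **1. The texts side by side**

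| | C.5.b | C.5.d, Study Design |
|---|---|---|
| Source | Due list for a first dose; also a registry cohort of about 1,038 | All who have not completed the series |
| Visit needed | No | Yes, the first in a 12-month window |
| Due condition | Explicit for the list; none for the cohort | None |
| Order of randomisation and a same-day dose | Not stated | Not stated |

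The cohort figure equals the whole age-eligible count in Table 2: 158 + 241 + 73 + 566 = 1038.

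**2. The plan's power figure**

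Inputs from Statistical Analysis and Power (C.5.d): 173 per arm (519/3), 33% vs 50%, significance level 0.05/3. Sidedness is not stated; two-sided is used, so z = 2.394. The two rates are given for series completion. For the next-dose endpoint the plan gives only the 0.17 difference, so they are borrowed here.

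Power = Φ(Δ/SE − z), with SE = √{[p₁(1−p₁) + p₂(1−p₂)]/n}.

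SE = √[(0.2211 + 0.2500)/173] = 0.0522. Then 0.17/0.0522 = 3.258, 3.258 − 2.394 = 0.864, and Φ = 80.6%. With a pooled variance the result is 79.6%. The stated 80% is reproduced.

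**3. Enrolment-visit doses (shares assumed)**

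Let a share s of each arm be vaccinated at the enrolment visit after randomisation. The rate in each arm becomes p = s + (1−s)p₀, so the difference becomes 0.17(1−s).

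| s | Usual care | Auto-Plus | Difference | Power, 173/arm | Power, 217–238/arm |
|---|---|---|---|---|---|
| 0 | 0.330 | 0.500 | 0.170 | 80.6% | 90–92% |
| 5% | 0.364 | 0.525 | 0.162 | 75% | 85–88% |
| 10% | 0.397 | 0.550 | 0.153 | 69% | 80–84% |
| 20% | 0.464 | 0.600 | 0.136 | 57% | 68–73% |

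The pooled formula gives 74, 68 and 56% at 173 per arm. The last column uses the non-completers implied by Table 2. Weighting clinic rates by clinic size, and assuming that ages 11–12 are 20 to 40% of ages 11–17, gives 651 to 713 non-completers, or 217 to 238 per arm. If 33% and 50% already include enrolment-visit doses, there is no loss in any row.

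**4. Attendance (share assumed)**

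The 519 is an age-eligible count with no allowance for non-attendance. If 90% attended in the window, 0.9 × 519/3 ≈ 156 per arm and power is about 76%. Against 651 to 713 the same loss leaves 195 to 214 per arm, above the 171 that give 80%.

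**5. Patients not yet due: a separate matter**

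Suppose 16% of participants are not yet due and keep half their response. At 217 per arm, keeping them multiplies both rates by 0.92 and power is 84.2%. Excluding them leaves 182 per arm and 82.9%. If they have no response at all, keeping them gives about 78%, against 82.9% without them. Exclusion can therefore lower or raise power.

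On the Table 2 weighting in step 3, 456 to 482 patients are uninitiated and 195 to 231 are initiated but incomplete. Reaching 519 needs 519 − 456 = 63 of the 195, or 519 − 482 = 37 of the 231, before removals for missing contact details or siblings.

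**The case against.** The strongest reply is that the visit phrase is loose wording for an index date. Eligibility is assessed before enrolment, C.4.b bases criteria on vaccine guidelines and treats clinic visits as a proxy for enrolment, and C.4.a leaves the trial protocol to be finalised after Bootcamp Translation. That may be so. But the current text gives two different entry events, and the time to choose is when the protocol is finalised.

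The attendance loss may be small. C.4.a describes about 1038 patients as meeting criteria that include a clinic visit in the last 12 months, and C.4.b uses visits in eligibility. This stands; what the visit rule adds is a new visit inside the study window.

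The dilution needs an order of events that the plan does not state: randomisation before the dose. This also stands, so the effect is conditional.

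A reader might infer that the visit rule lets in patients who are not yet due. The documents do not support that. The issue arises from the population of all non-completers in C.5.d, and the C.5.b cohort has no due filter either. Deleting the visit phrase would not change it. Nor is C.5.c a competing entry rule, since it never mentions randomisation.

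**Conclusion.** The conflict between C.5.b and C.5.d over what triggers entry is real and unreconciled, and it should be settled before the first randomisation. Read literally, C.5.d narrows the population to attenders in the window. If randomisation precedes the visit's dose, it also dilutes the 6-month comparison.

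The size is not determined by the documents. Every share above is assumed, and the 33% and 50% come from the completion endpoint. At 173 per arm there is almost no reserve, so 5 to 20% enrolment-visit doses would mean about 75 to 57% power. At the 217 to 238 per arm implied by Table 2, power falls below 80% only above a share of about 10 to 14%.

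Two stronger conclusions are tempting and not supported. One is that the comparison is biased or its type I error inflated: enrolment-visit doses are expected equally in all arms. The other is that the trial is shown to be underpowered: no share is documented, and the planned rates may already include such doses. Confidence in the point is medium.

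**What to change.** Reconcile C.5.b and C.5.d to one entry rule:

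- Randomise from the planned electronic due list or registry list, independently of any visit, and delete the first-visit wording in C.5.d. Rolling entry over 12 months from a refreshed list still fits the 25-month timetable.
- Make the randomisation date time zero for the 6- and 13-month endpoints.
- Count only doses given after randomisation, by the same rule in every arm. Independence from visits is the essential part, because a dose given later in an enrolment visit would still pass this count.
- Keep everyone randomised in the analysis. Opportunistic doses after randomisation will still occur in all arms and belong in the outcome.

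Separately, state whether initiated patients who are not yet due enter at once or when they become due, and check the 519 against that choice. Restricting entry to due patients is a trade-off (step 5 of the working) and is not required. No vaccine schedule is changed or proposed.

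The cost is protocol wording, and possibly later entry for some patients. The lists are already planned, and C.7 offers additional clinics if recruitment is slow.

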## C. APPROACH

C.1. Project Overview: This two-stage study was designed in collaboration with Sea Mar Community Health Centers, an active member of [name] IMW HPV Vaccination Coalition. 65 The proposed project optimally aligns with the expertise of the study team and leverages our clinic partner's commitment to improving HPV vaccination and reducing disparities in HPV-related cancer incidence and mortality. Our study will test automated and live reminders for HPV vaccination (Figure 4). In Phase I (Years 1-2), we will refine intervention components and messages to increase HPV vaccination among rural C/A. We will use a validated patient-engaged approach for P/Cs, BCT, with separate sessions conducted in English and Spanish. In Phase II, we will conduct a P/C randomized controlled trial (RCT) that tests automated strategies (e.g., automated phone calls,

[figure not shown]

Figure 4. PREVENT Study Design.

EHR = electronic health records; RCT = randomized controlled trial; HPV = human papillomavirus

text messages) and combined automated and interactive live strategies to prompt P/Cs of vaccine-eligible C/A to complete the next dose of the HPV vaccine (i.e. first, second, or third dose depending on age of C/A). The individual-RCT will include P/Cs of 1038 vaccine-eligible patients at 4 rural clinics in Washington (Rural-Urban Continuum Codes of 3-9). This trial could significantly reduce HPV-associated cancer disparities and can be sustained long-term.

C.2. Research Team and Preliminary Data: Our multidisciplinary team includes investigators with a record of developing and testing multiple cancer prevention interventions; analysts with years of experience designing registries and reminder and recall systems; implementation scientists; and qualitative researchers. [name] will lead this project in partnership with [name] and [name], Medical Director at Sea Mar,

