rural Utah, Colorado, Nevada, Montana, and Arizona (N=140 participants; 3P30 CA042014-2958). Focus groups assessed system-level barriers and needed adaptations for implementing evidence-based HPV vaccination strategies in rural primary care clinics (**Table 1**).84 The findings underscore P/Cs' uncertainty about which vaccines to get and providers' and stakeholders' desire for systems to remind P/Cs to obtain the vaccine. [name] hosts monthly video-call meetings with partners (**Letters of support**).65,82

Table 2. Selected Sea Mar Community Health Center Clinics\*

Sea Mar Clinic Location	N patients (2019)	% Rural	% His- panic	N patients ages 11-17 years	Among Patients Ages 11-12 Yrs.*		Among Patients Ages 13-17 Yrs.*	
					% HPV vac. Initiat.	% HPV vac. complet.	% HPV vaccine initiat.	% HPV vaccine complet.
Ocean								
Shores	2971	40.1	5.6	158	36.7	2.6	45.5	25.6
Aberdeen	3941	40.1	14.9	241	45.4	8.5	62.1	44.8
Elma	982	40.1	21.8	73	53.3	16.3	74.7	67.7
Yelm	4088	29.0	13.0	566	48.3	18.2	58.5	44.3

\*Estimated 5% decline in HPV vaccination rates shown due to COVID-19 pandemic challenges

[name], an epidemiologist, is bilingual in English and Spanish and a national leader in practice-based cancer prevention research in safety net clinics. [name] and her team have established formal collaborations

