# C.5. Aim 2: Test a set of automated reminders (defined during Aim 1) on timely receipt of next needed HPV vaccine dose and on series completion.

We hypothesize that Auto and Auto-Plus interventions will be more effective than usual care, and Auto-Plus will be more effective than Auto at increasing receipt of the next needed HPV vaccine dose and on series completion. We will implement and evaluate the intervention in 4 clinics using an individual-RCT design (IM Steps 5 and 6). Our quantitative evaluation will assess intervention effectiveness and reach. We will gather P/C-, patient- and HCP-level data to identify possible program enhancements, as well as barriers and facilitators to adoption, implementation, and maintenance.

**C.5.a.** Convene Teams and Train Staff: Each participating clinic will convene an implementation team comprised of a clinic champion, clinic coordinator, and relevant laboratory and administrative personnel whom we will select for their ability to facilitate the intervention within the clinic settings. Once the team is formed, members of the PREVENT research team and clinic staff will train the participating clinics in delivering the intervention. Staff training will take place during a half-day session (with additional phone support) and will address procedures for identifying P/C of eligible patients and tracking automated outreach (e.g., automated phone calls, text messages). Clinics will receive training specific to the Auto-Plus components, such as the live phone call and patient navigation protocols using as computer assisted interactive system.

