Statistical Approaches: The primary comparisons are between the rates of completing the next step in the HPV vaccination series at 6 months in the Auto, Auto-Plus, and UC arms (Primary Outcome), and between the rates of completing the HPV vaccination series at 13 months (Secondary Outcome). Completing the next step in the vaccine series and completing the vaccine series outcomes will be compared via logistic generalized estimating equations (GEE) models, 129, 130 with bias-reduced robust sandwich variance estimators 131 clustered by clinic. These logistic GEEs will be adjusted for P/C and patient features that may influence HPV vaccination series next step and completion, including age, sex, race/ethnicity, rurality, and HPV vaccination initiation status at study enrollment. Models comparing the Auto, Auto-Plus, and UC groups, will also include study arm. Comparisons between the study arms of the next-step and series-completion endpoints will be performed separately. For each endpoint, pairwise differences between arms will be assessed with a Bonferroni correction to achieve type I error control at 0.05, with p<0.017=0.05/3 needed for statistical significance. Predefined subgroup analyses will be performed by P/C and/or patient sex, age group, race/ethnicity, rurality, and HPV vaccination initiation status at study enrollment, and each of these characteristics will be assessed for effect moderation. Since next step completion and series completion will be captured via the EHR and the state-wide vaccine registry, we anticipate little missing data for these outcomes. Statistical Analysis and Power: Based on the **Table 2**, there are 1038 patients in the appropriate age range, of whom <50% will have completed the HPV vaccination series, for at least 519 patients within the eligible age range who have not yet completed the HPV vaccination series, with at least 173 in each study arm. 173 participants per study arm will ensure >80% power for detecting rate differences for both the next step endpoint and series completion endpoint exceeding 0.17, under the Bonferroni statistical significance benchmark of p<0.017. If the completion endpoint rate is 50% in the Auto-Plus arm and is 33% in the UC arm (rate difference 0.17), then the proposed study will have 80% power for detecting a difference by arm. Moderators: We will assess differences across study arms in our secondary outcome: missed opportunities, defined as patients who receive other recommended vaccinations, but not HPV. We will also explore possible moderators of effectiveness: age (11– 14, 15–17), ethnicity (Hispanic vs. non-Hispanic white), sex (male vs. female vs. other), language (Spanish vs. English), poverty status (<100% Federal Poverty Level vs ≥100% Federal Poverty Level), and insurance status (commercial vs. Medicaid vs. other). Thus, we will consider **sex a biological variable**, an important distinction because of differing rates of HPV vaccination and barriers faced by adolescent males and females. 132-135 By assessing differences in effectiveness across the life course of ages 11-14 and 15-17, we will understand differences in groups for whom 2 doses and 3 doses of the vaccine is recommended. Each potential moderator will be tested separately by considering its main effect and interaction with study arm in the logistic mixed effects models (Aim 2). Evidence of differential intervention effectiveness will be supported by an overall test of

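### The variance of every arm comparison is clustered on 4 very unequal clinics with no reference distribution named, so either the 0.017 threshold does not hold or the stated 80% power falls to about 34%

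*Combined protocol and SAP*

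**What the plan says.** The trial is individually randomised: "We will implement and evaluate the intervention in 4 clinics using an individual-RCT design" (C.5 Aim 2). Allocation is 1:1:1, "with separate randomizations within each clinic (Ocean Shores, Aberdeen, Elma, or Yelm", and by initiation status (C.5.d, Study Design). C.5.b gives a different set of strata: "stratified by clinic, sex, and language preference (English, Spanish, other".

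Under Statistical Approaches in C.5.d, both the 6-month and the 13-month outcome are compared by logistic GEE "with bias-reduced robust sandwich variance estimators 131 clustered by clinic". Each endpoint has three pairwise tests, "with p<0.017=0.05/3 needed for statistical significance". No reference distribution, degrees of freedom or working correlation is given. The covariates named are age, sex, race/ethnicity, rurality and initiation status. The list is not worded as exhaustive, but neither clinic nor language preference is on it.

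On power, the same section says "173 participants per study arm will ensure >80% power for detecting rate differences" above 0.17, with 50% versus 33% as the example. C.1 gives a larger total: "The individual-RCT will include P/Cs of 1038 vaccine-eligible patients at 4 rural clinics in Washington". Table 2 lists 158, 241, 73 and 566 patients aged 11–17 at Ocean Shores, Aberdeen, Elma and Yelm.

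**The concern.** A variance clustered by clinic is built from one summed contribution per clinic, so here from 4. Yelm supplies 566/1038 = 55% of the patients and Elma 73/1038 = 7%. The bias reduction corrects the average of that variance. It does not make an estimate from 4 unequal pieces stable, and the effective degrees of freedom are about 1.9.

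The critical value therefore decides the outcome, and the plan does not give one. A normal value ignores the instability and rejects too often. A small-sample t value largely restores the error rate but costs most of the power. This applies to every confirmatory comparison on both endpoints, and the choice would be made when the data are analysed.

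The clustering also does not follow from the design. Arms are balanced within clinic, so whatever patients at a clinic share cancels from the arm contrasts.

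**Working it through.** **1. The plan's own figure.** Inputs from C.5.d: rates 0.50 and 0.33, 173 per arm, alpha 0.05/3. Sidedness is not stated; two-sided is assumed (one-sided would give 86%). The critical z is 2.394.

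- SE (unpooled) = √[(0.50×0.50 + 0.33×0.67)/173] = √(0.4711/173) = 0.0522.
- Power (unpooled) = Φ(0.17/0.0522 − 2.394) = Φ(0.864) = 80.6%.
- Power (pooled null variance) = 79.6%.

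So the stated 80% is an individual-level two-proportion calculation with a normal critical value. Clinic plays no part in it.

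**2. A rough check of the t reference.** The t(3) critical value at alpha 0.05/3 is 4.857. With noncentrality 0.17/0.0522 = 3.26 on 3 df, noncentral-t power is 30% at 173 per arm. At 346 per arm (N = 1038) it is 55%.

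**3. Simulating the written analysis.** Table 2 scaled to 173 per arm (divide by 6, then round) gives 27/40/12/94. The model is a logistic GEE with independence working correlation and the Bell–McCaffrey (CR2) sandwich on 4 clinics. With 200,000 replicates of the arm-only model:

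- normal reference: 11.8% error per pair, 77% power;
- t(3): 2.3% error per pair, 33.7% power;
- model-based individual-level variance on the same data: 1.6–1.8% error, about 79% power.

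The three-arm model with covariates and clinic differences (3,000 runs per setting, 1:1:1 within clinic and initiation status, clinic intercept SD 0.3 on the logit, half already initiated, Auto at 41.5%) was run at three totals because the documents give more than one. N = 519 and 1038 assume equal eligibility across clinics. N = 677 applies Table 2 completion rates with an assumed 2/7 of patients aged 11–12 and 5/7 aged 13–17. Error ranges span the three totals.

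| Variance and reference | Error per pair | Error, any pair | Power at N = 519 / 677 / 1038 |
|---|---|---|---|
| CR2, normal | 11–13% | 28–30% | not a valid comparison |
| CR2, t(3) | 1.9–2.9% | about 6–7% (N = 519) | 34 / 43 / 59% |
| CR2, Satterthwaite df (median 1.9) | 0.3–0.7% | not computed | 13 / 17 / 26% |
| Mancl–DeRouen, normal | 7–8% | 19–21% | not a valid comparison |
| Clinic fixed effects, participant-level SE | 1.4–2.4% | 4.0–5.5% | 81 / 91 / 98% |

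Monte Carlo standard error is about 0.6 points for error near 12% and about 0.9 points for power.

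**4. Precision.** The planned effect is a log odds ratio of ln(0.50/0.50) − ln(0.33/0.67) = 0.71. The median interval half-width at N = 519 is 0.45 (CR2, normal), 0.92 (CR2, t(3)) and 0.55 (clinic fixed effects). A typical t(3) interval around the planned effect would therefore include zero.

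**5. Sensitivity.**

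- Four equal clinics: 9.6% error (normal) and 28% power (t(3)).
- Weighting clinics by estimated non-completers (33/40/9/91 per arm): 12.0% and 34.2%.
- Between-clinic base-rate SD of 0.3–0.6 on the logit: about 12% error and 32–33% power.
- Exchangeable working correlation with the Mancl–DeRouen correction: 7.7% and 22%.

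**The case against.** The strongest objection is that clustering by clinic is an estimand choice, not a mistake. The protocol looks to wider dissemination, and clinic staff deliver Auto-Plus, so effects may differ by clinic. If the null is a zero average effect over a population of clinics, the fixed-effect test is the less protective one.

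- With an assumed arm-by-clinic logit SD of 0.2 it rejects about 3% of the time for an active arm versus usual care; with 0.4, about 9%.
- For Auto-Plus versus Auto it rejects 6% and 17% if the clinic deviations of the two arms are independent, and 3.4% and 9.7% if they correlate at 0.5. Positive correlation is plausible because Auto-Plus contains Auto.
- At SD 0.4 with independent deviations, CR2 with t(3) gives 2.7–3.3% per pair and 8.6% for any pair, against 25.5% for any pair with fixed effects.
- CR2 with normal critical values rejects 13–14% per pair at SD 0.2–0.4.

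This stands as a limit on what the fixed-effect model can claim. It does not rescue the plan, because 4 clinics cannot support the wider inference with useful power.

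It is also fair that the plan never says it will use normal critical values. The 12% and 29% are conditional on that choice, and they would breach the plan's own commitment to 0.05. But the alternative forfeits the stated power, and t(3) itself leaves about 6–7% error over the three pairs.

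Reserve clinics are mentioned in C.3.a and C.7. With the same total N in 12 equal clinics, CR2 with t(11) gave 1.0–1.9% error and 62% power; with 20 clinics, power was 69%. That is a different and more costly design than the one written.

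**Conclusion.** The analysis is wrong as written. With 4 clinics as variance clusters, no choice of reference distribution delivers both the 5% error control and the 80% power that C.5.d states. Normal critical values give about 12% error per pair and about 29% over three pairs; t(3) gives about 34% power at 173 per arm and 59% even at 1038 in total; Satterthwaite degrees of freedom give 13% and 26%.

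The headline figures assume the CR2 form of bias reduction, an independence working correlation, Table 2 clinic proportions, two-sided tests and no variation of the effect between clinics. Other corrections, equal clinics, covariates and base-rate differences move the figures but not the conclusion. The fixed-effect model's power at N = 519 also depends on assumptions: 81% in the main setting and 77% with a weaker covariate effect. It should be described as roughly 77–81%.

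**What to change.** In C.5.d, replace the clinic-clustered GEE with a logistic model that has:

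- clinic as a fixed effect;
- the other randomisation strata (initiation status, and sex and language preference once C.5.b and C.5.d are reconciled);
- the listed covariates;
- model-based or participant-level robust standard errors.

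State that the estimand is the average effect in these 4 clinics. Use the same model for the moderator tests, which now refer to logistic mixed effects models that the plan does not otherwise define. Restate the power for this model at one reconciled total, since the documents give both at least 519 and 1038. A randomisation test stratified by clinic would also fit the design.

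If clustering by clinic is kept, name the t reference and its degrees of freedom, and report the power and the three-pair error under it.

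The cost is SAP wording only, with no change to trial conduct. The price is narrower inference: it covers these 4 clinics, and the report should say so.
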